7.3.5 Day 4 (Day of Discharge)

1. Symptom-directed physical examination
2. Vital signs
3. Oximetry
4. Review of concomitant medications
5. AE review
6. Spirometry
7. Obtain blood and urine samples for local laboratory assessments
8. Obtain blood and sputum samples for inflammatory biomarkers
9. Obtain the following samples for PK:
 - Blood at 54 and 72 hours post dose
 - Urine at 72 hours post dose

- Sputum at any time prior to discharge

10. Discharge subject

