7.1 Visit and Assessment Windows

The flexibility regarding scheduling of study days and corresponding procedures differ depending on the cohort and phase of the study. The timing of assessments, procedures and sample collections outlined in the protocol are nominal times. It is understood that in the phase 1 setting, actual times will approximate rather than match the nominal times exactly. Actual times are to be recorded in the source documentation and in the case report forms (CRFs), and, if any time points are missed, the reasons are also recorded.

For the SAD cohorts, there is no flexibility regarding the timing of the scheduled study days in relation to dose Day 1.

For the MAD cohorts, there is some flexibility regarding the timing of the scheduled study days in relation to dose Day 1. The description of procedures assumes a Monday-Wednesday-Friday dosing schedule. An alternative dosing schedule can be used, provided that there is at a minimum 2 days between doses, and a maximum of 4 days between doses. Missed doses are to be recorded as such, and the overall treatment period should remain at 4 weeks, and not be extended to accommodate the missed doses. Missed doses are to be recorded in the CRF.

Details regarding acceptable windows for timing of study procedures for both the SAD and MAD cohorts can be found in the Laboratory Manual.

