5. AE review
6. Spirometry at 10, 30, and 60 minutes, and 2, 4, and 8 hours post dose
7. Obtain blood samples for local laboratory assessments at 30, 60 minutes, 2, 4, 8, and 12 hours post dose
 - Complete blood count (CBC) with absolute differential
 - Serum chemistry
8. Obtain the following samples for PK:
 - Blood at 0.5, 1, 2, 3, 4, 12 hours post dose
 - Pooled urine from 0 to 4 hours, 4 to 12 hours, and 12 to 24 hours post dose. Subjects should empty their bladders just prior to dosing and at the end of each time interval for the final urine collection of that interval. Urinalysis by dipstick will be performed on the pooled urine samples for each time interval.
 - Sputum at 3 times post dose, within the first 6 hours post dose. Suggest obtaining samples in conjunction with performing spirometry at 10, 60 minutes, and 4 hours post dose.

7.3.3 Day 2

1. Symptom-directed physical examination
2. Vital signs
3. Oximetry

4. Review of concomitant medications
5. AE review
6. Spirometry
7. Obtain blood and urine samples for local laboratory assessments 24 hours post dose
8. Obtain the following samples for PK:
 - Blood at 24 hours post dose
 - Urine at 24 hours post dose
 - Sputum at 24 hours post dose
9. Obtain blood and sputum samples for inflammatory biomarkers (24 hours post dose)

7.3.4 Day 3

1. Vital signs
2. Oximetry
3. Concomitant medications review
4. AE review
5. Obtain blood and urine samples for local laboratory assessments 48 hours post dose
6. Obtain the following samples for PK:
 - Blood at 48 hours post dose
 - Urine at 48 hours post dose

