18.0 APPENDICES

Appendix 1 Schedule of Assessments

Appendix 2 Schedule of Laboratory Assessments

Appendix 3 CFQ-R, Adult Version (English)

APPENDIX 1: SCHEDULE OF ASSESSMENTS

Table A.1-1: Single Ascending Dose Cohorts 1-4

| Study Procedures | Screening | Check-In | | | | Discharge | | | | End of Study |
|----------------------------------------|-----------------------|----------------|----------------|----|----|-----------|----|-----|-----|----------------|
| Study Day | ≤14 days ^a | -1 | 1 ^b | 2 | 3 | 4 | 5 | 6 | 7 | 8 |
| In Hours | | -24 | 0 | 24 | 48 | 72 | 96 | 120 | 144 | 168 |
| Informed consent | X | | | | | | | | | |
| Demographics | X | | | | | | | | | |
| Medical History | X | | | | | | | | | |
| Eligibility Review | X | X | | | | | | | | |
| Concomitant Medications | X | X | X | X | X | X | | | | X |
| Adverse Events | | X | X | X | X | X | | | | X |
| Physical Exam | C | C | S | S | | S | | | | C |
| Height & Weight | H/W | W | W | | | | | | | W |
| Vital Signs ^c & Oximetry | X | X | X | X | X | X | | | | X |
| Spirometry ^d | X | X | X | X | | X | | | | X |
| Chest Xray | X ^e | | | | | | | | | X ^f |
| 12-lead ECG | X | | | | | | | | | X |
| 24-Hour Telemetry | | | X | | | | | | | |
| Blood for Safety Labs ^g | X | X ^h | X | X | X | X | | | | X |
| Urinalysis ^g | U | U ^h | U | U | U | U | | | | U |
| Drug Screen ^g | X | | | | | | | | | |
| Pregnancy Test ^{g,i} | X | X | | | | | | | | X |
| Sputum for Microbiology ^g | | X | | | | | | | | X |
| Blood for CFTR ^g | Genotyping | Sequencing | | | | | | | | |
| Biomarkers ^g | X | X | | X | | X | | | | X |
| Sweat Chloride ^g | X | | | | | | | | | |
| Randomization | | X | | | | | | | | |
| Study Drug Administration ^j | | | X | | | | | | | |
| Collect Samples for PK ^g | | | X | X | X | X | | | | X |

Abbreviations: C = complete physical exam; H = height; S = symptom-directed physical exam; U = urinalysis (dipstick); W = weight

^a The screening period for an individual subject may be extended for an additional 7 days at the discretion of the Sponsor's Medical Monitor. See Section 7.2 for details.

^b See Section 7.3.2 for details on timing of these assessments relative to study drug administration on Day 1.

^c Includes blood pressure, heart rate, respiratory rate, and temperature.

^d Includes FEV₁, FVC, and FEF₂₅₋₇₅.

^e A Chest Xray or CT scan obtained within 90 days of screening is acceptable if there was no intercurrent pulmonary illness during the interim.

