APPENDIX 2: SCHEDULE OF LABORATORY TESTS

Table A.2-1: Single Ascending Dose Cohorts 1-4

| Labs | Screening | Check-In | Dose | | | Discharge | | | End of Study ^a | |
|----------------------------------------------------------------|-----------------------------------------------------------------------------------------------------------------------------------------------------------------------------------------------------------------------------------------------------------------------------------------------------------------------------------------------------------------|----------------|----------------|----|----|----------------|----|-----|---------------------------|----------------|
| Study Day | ≤-14 days ^b | -1 | 1 | 2 | 3 | 4 | 5 | 6 | 7 | 8 |
| In Hours | | -24 | 0 | 24 | 48 | 72 | 96 | 120 | 144 | 168 |
| Hematology | X | X | X | X | X | X | | | | X |
| Serum Chemistry | X | X | X | X | X | X | | | | X |
| Hematology & Chemistry | Day 1: Pre-dose, 30, 60 minutes, 2, 4, 8, 12 hours post dose | | | | | | | | | |
| C-Reactive Protein | | X | X | X | | | | | | X |
| Erythrocyte Sedimentation Rate | | X | X | X | | | | | | X |
| C-Reactive Protein & Erythrocyte Sedimentation Rate | Day -1 Day 1: Pre-dose, 24 hours post dose | | | | | | | | | |
| Coagulation and CH50 | X | | | | | | | | | X |
| Direct Antiglobulin Test | X | | | | | | | | | X |
| Serum Tocopherol (Vit. E) | X | | | | | | | | | |
| Urine microalbumin | | X | | | | | | | | X |
| Urinalysis | X | X | X | X | X | X | | | | X |
| | Day 1: On pooled PK samples Day 2, 3, 4, 8: Random sample, preferably 1 st morning void | | | | | | | | | |
| Drug Screen | X ^c | | | | | | | | | |
| Pregnancy test ^d | X | X | | | | | | | | X |
| Sputum for Microbiology | | X | | | | | | | | X |
| CFTR Genotyping ^e | X | | | | | | | | | |
| CFTR Sequencing | | X ^f | | | | | | | | |
| Sweat Chloride | X | | | | | | | | | |
| PK Sampling | Serum: 0, 0.5, 1, 2, 3, 4, 12, 24, 48, 54, 72, 168 hours post dose Urine: Pre-dose; Pooled from 0 to 4, 4 to 12, and 12 to 24 hours post-dose; and 48, 72, and 168 hours post dose (UA on each pooled sample). Sputum: 3 samples obtained within first 6 hours post dose; 24 hours post dose; Day 4 (72 hours post dose); and Day 8 (168 hours post dose) | | | | | | | | | |
| Serum for PK | | | X | X | X | X | | | | X |
| Urine for PK | | | X | X | X | X | | | | X |
| Sputum for PK | | | X ^g | X | | X ^h | | | | X ^g |

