#### **4.9. Pharmacokinetic Evaluations**

In the SAD portion of the study, sample collections for support of PK analysis are planned as follows:

- Blood (i.e. serum): pre-dose (time 0), 0.5, 1, 2, 3, 4, 12, 24, 48, 54, 72, 168 hours post-dose.
- Urine: Pre-dose (time 0); Pooled from 0 to 4, 4 to 12, and 12 to 24 hours post-dose; and 48, 72, and 168 hours post dose.
- Sputum: 3 samples obtained within first 6 hours post dose; 24 hours post dose; Day 4 (72 hours post dose); and Day 8 (168 hours post dose)

In the MAD portion of the study, sample collections for support of PK analysis are planned as follows:

Week 1, Dose 1

- Serum: 0, 0.5, 1, 2, 3, 4, 12; pre-Dose 2 (48 hours post-dose 1)
- Urine: Pre-dose; Pooled from 0 to 4 and 4 to 12 hours post Dose 1.
- Sputum: pre-dose, 3 samples obtained within first 6 hours post Dose 1.

Week 4, Dose 12

- Serum: pre-dose (0), 1, 2, 3, 4, 8, 24, 96, 144 (7 days post-last dose) and 648 hours (28 days post-last dose).
- Urine: Pre-dose; 24 and 96 hours, post-dose.

Additional sample collections are planned on interim study days during the MAD portion of the study. The measured concentrations will be presented in listings and used to confirm adequate QR-010 exposure; however, they will not be used to support generation of PK parameters. Additionally, urine concentrations that did not come from pooled collections or for which sample volumes were not collected will only be displayed in listings and will not be used to support generation of renal PK parameters.

The planned PK parameters for each portion of the study may be found in Table 26 below. Area under the serum concentration curve (AUC) will be generated using the linear-log trapezoidal rule.

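### The 54 h SAD serum PK sample is listed under Day 4, but the protocol's own grid puts it on Day 3, so it may be drawn late or missed

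*Protocol*

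**What the plan says.** Protocol 7.3.4 (Day 3) lists PK "Blood at 48 hours post dose" and no other PK blood sample. Protocol 7.3.5 (Day 4, day of discharge) lists "Blood at 54 and 72 hours post dose". The day and hour rows of Tables A.1-1 and A.2-1 set Day 1 at 0 h, Day 2 at 24 h, Day 3 at 48 h, Day 4 at 72 h and Day 8 at 168 h.

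Table A.2-1 keeps 54 h as a separate time ("Serum: 0, 0.5, 1, 2, 3, 4, 12, 24, 48, 54, 72, 168 hours post dose"), and so does SAP 4.9 ("pre-dose (time 0), 0.5, 1, 2, 3, 4, 12, 24, 48, 54, 72, 168 hours post-dose"). Neither ties it to a day: Table A.2-1 only marks serum PK on Days 1, 2, 3, 4 and 8.

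On timing, Protocol 7.1 says that for SAD "there is no flexibility regarding the timing of the scheduled study days in relation to dose Day 1". It also treats listed times as nominal ("actual times will approximate rather than match the nominal times exactly"), has actual times recorded in source and CRF, and leaves procedure windows to the Laboratory Manual, which is not among the documents. Protocol 4.2 keeps SAD subjects under inpatient observation until discharge on Day 4.

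**The concern.** For ordinary dosing times, no draw can be both on Day 4 and at 54 h. A coordinator using 7.3.4 as the Day 3 checklist finds no 54 h sample on it. When the Day 4 list comes into use, 54 h has already passed. The likely results are a late draw, two nearly coincident Day 4 draws, or a missed sample.

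At stake is the terminal phase. In SAP Table 26, T1/2 and AUCinf appear for SAD only. Both rest on lambda z, and so on the late serum samples. After 24 h there are four (48, 54, 72 and 168 h), and 54 h is the only one strictly between 48 and 72 h. PK is a secondary objective of the study.

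A second risk is labelling. Protocol 13.8 summarises concentrations by nominal time point, and SAP 4.9 does not say whether lambda z and AUC use nominal or actual times. A draw made at about 72 h could therefore be analysed as a 54 h value.

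**Working it through.** **1. Day on the protocol's own grid.** Study day = floor(hours/24) + 1, which reproduces the day and hour rows of Table A.1-1.

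| Listed under | Serum hours | Computed day |
|---|---|---|
| Day 1 (7.3.2) | 0, 0.5, 1, 2, 3, 4, 12 | 1 |
| Day 2 (7.3.3) | 24 | 2 |
| Day 3 (7.3.4) | 48 | 3 |
| Day 4 (7.3.5) | 54 | floor(2.25) + 1 = **3** |
| Day 4 (7.3.5) | 72 | 4 |
| Day 8 (7.3.6) | 168 | 8 |

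Eleven of the 12 times match their listed day. The 54 h time does not: it is 6 h after the Day 3 time and 18 h before the Day 4 time.

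**2. Calendar day.** The documents give no clock time for dosing, so this is an assumption shown over a range. With dosing at clock hour c, the calendar day of the 54 h draw is floor((c + 54)/24) + 1. That equals 4 only if c + 54 ≥ 72, that is c ≥ 18.
- Dose at 09:00: 9 + 54 = 63, which is 15:00 on Day 3.
- Day 4 begins 72 - c hours after dosing. For a 09:00 dose that is 63 h, so a Day 4 draw is at least 63 - 54 = 9 h late.
- Doses from 07:00 to 10:00: Day 4 begins at 65 to 62 h, so a Day 4 draw is at least 11 to 8 h late. A draw at 08:00 on Day 4 is at 73 to 70 h.

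**3. Points remaining.** If the 54 h draw is made at about 72 h or missed, distinct serum times fall from 12 to 11. Those at or after 48 h fall from four to three (48, 72, 168 h).

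**4. Lambda z if a 72 h value is modelled at 54 h.** Assume first-order decline at rate k, so log concentration is linear in time. The value labelled 54 h is then too low by 18k on the log scale. Least squares gives

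estimated λz / true λz = 1 + 18 × (54 - m) / S,

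where m is the mean of the nominal times and S their sum of squared deviations.

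| Fit times (h) | m | S | Ratio | Error in λz |
|---|---|---|---|---|
| 24, 48, 54, 72, 168 | 73.2 | 12412.8 | 1 - 345.6/12412.8 = 0.97 | -3% |
| 24, 48, 54, 72 | 49.5 | 1179 | 1 + 81/1179 = 1.07 | +7% |
| 48, 54, 72 | 58 | 312 | 1 - 72/312 = 0.77 | -23% |

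The ratio does not depend on k, so it holds for any first-order half-life. With the actual time entered, the value lies on the line and the ratio is 1.

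**5. AUC if the point is simply missing.** The SAP's linear-log trapezoid is exact over 48 to 72 h for a mono-exponential decline, so nothing is lost there. Protocol 13.8 names the linear trapezoid instead. The half-life is not given; for assumed values of 12, 24 and 48 h, the linear rule without the 54 h point overstates the 48 to 72 h segment by about 16%, 4% and 1% (with the point, 6%, 2% and 0.4%). For a mono-exponential curve from time 0, that segment is 4.7%, 12.5% and 14.6% of AUCinf. The error in AUCinf is then about 0.155 × 0.047 = 0.7%, 0.040 × 0.125 = 0.5% and 0.010 × 0.146 = 0.1%.

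**The case against.** The best defence is that the correct hour is printed in the criticised line and again in Table A.2-1 and SAP 4.9. The line gives 54 and 72 h as two separate draws, and the subject is an inpatient at 54 h. A site working by hours after dose takes the sample on Day 3 without difficulty. The day lists are also not strictly calendar-bound: the Day 1 list carries a 12 to 24 h urine collection that can end on Day 2. Actual times are recorded, so a late draw can be identified and modelled where it belongs.

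Most of this stands, and it makes the late or missed sample a risk rather than an outcome. It does not remove the contradiction. A collection that starts on Day 1 and runs on is easy to follow, whereas a sample listed under a day that begins after it is due is easy to miss. Recording actual times cannot restore a point that was never drawn at 54 h.

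A reader might infer three stronger things that the documents do not support:
- That the point is bound to be lost. The printed hour and the inpatient stay argue against this.
- That all the clearance and volume results hang on SAD. SAP Table 26 also plans CL/F and V/F for MAD dose 12, from AUCtau; only T1/2 and AUCinf are confined to SAD.
- That losing 54 h, with 168 h below quantification, leaves too few points by the SAP's own rule. The three-point minimum is written for estimating the 48 h concentration after MAD dose 12. Nothing excludes the 24 h sample from the SAD fit, so 24, 48 and 72 h would remain.

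**Conclusion.** The day assignment is wrong as written: 54 h is Day 3 on the protocol's grid, and on the calendar for any dose before 18:00. Sections 7.3.4 and 7.3.5 and Table A.2-1 need to be reconciled. The consequence is a possible late or missed sample at the only planned serum time between 48 and 72 h.

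The size is limited. A missing point costs one of four times at or after 48 h and has little effect on AUC under the assumptions above. The lambda z errors of -3%, +7% and -23% need two events together: a draw at about 72 h, and modelling at nominal 54 h. The documents do not say that nominal times are used for lambda z. The largest figure also needs the narrow 48 to 72 h window; the two wider fits err slightly, in opposite directions. The calculation assumes first-order decline over the fitted window. This is a minor point that is cheap to correct.

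**What to change.** In Protocol 7.3.4, list PK blood at 48 and 54 h post dose under Day 3; in 7.3.5, leave PK blood at 72 h only. In Table A.2-1, which the SAP appendix repeats, state that 48 and 54 h belong to Day 3.

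In SAP 4.9, state that actual sampling times are used for lambda z and AUC, and that any sample labelled 54 h but taken on Day 4 is identified in the listings and left out of the 54 h nominal-time summary. For samples already collected, this SAP change is the part that still helps.

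The cost is a few lines of text. No draw or visit is added, because SAD subjects are in the unit until Day 4.

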7.3.6 Day 8 End of Study Visit

If at any time during the study the subject discontinues the study early, the subject should return to the clinic to complete the End of Study Visit procedures below.

1. Complete physical examination (including body weight)
2. Vital signs
3. Oximetry
4. Concomitant medications review
5. AE review
6. Chest Xray for subjects who experience pulmonary AEs during the study
7. 12-lead ECG
8. Spirometry
9. Obtain blood and urine samples for local laboratory assessments
10. Obtain urine or blood sample for pregnancy test (for women of child-bearing potential)
11. Obtain blood, urine, and sputum samples for PK 168 hours post dose. Sputum for PK may be obtained at any time during the visit.
12. Obtain sputum sample for the following local laboratory assessment:
 - Microbiology organism identification
13. Obtain blood and sputum samples for inflammatory biomarkers

7.4 MAD Cohorts (Cohorts 5-8)

7.4.1 Dosing Schedule

Study drug will be administered in the clinic for all dosing days. The dosing schedule below assumes a Monday-Wednesday-Friday (thrice-weekly or tiw) dosing scheme. Subjects will be observed until 12 hours post dose on Day 1 and Day 3. The subject will return to the clinic for all subsequent doses and required assessments.

7.4.2 Day -1

1. Confirm study eligibility
2. Complete physical examination (including body weight)
3. Vital signs: blood pressure, heart rate, respiratory rate, and temperature measured
4. Oximetry

5. Concomitant medication review
6. AE review
7. Obtain blood and urine for local laboratory assessments (only assessments that were abnormal but not clinically significant at screening)
8. Obtain urine or blood for pregnancy test (for women of child-bearing potential)
9. Obtain sputum sample for the following local laboratory assessment:
 - Microbiology organism identification
10. Obtain blood samples for CFTR sequencing (required, separate consent form may be required). Note: this blood sample may be collected on Day 1 pre-dose instead of Day -1, and should not be collected if subject already participated in a SAD cohort.
11. Obtain blood and sputum samples for inflammatory biomarkers. Note: these blood and sputum samples may be collected on Day 1 pre-dose instead of Day -1.
12. Spirometry (FEV₁, FVC, and FEF₂₅₋₇₅) post administration of short-acting bronchodilator

7.4.3 Week 1, Day 1 (Dose 1)

Pre-dose:

1. Subject self-completes the CFQ-R prior to all other procedures and assessments
2. Symptom directed physical examination (including body weight)
3. Vital signs
4. Oximetry
5. Concomitant medications review
6. AE review
7. Administer any routine pulmonary medications and airway clearance techniques, including SABA and/or LABA, Pulmozyme, inhaled corticosteroids and/or antibiotics
8. Initiate continuous cardiac and vital signs monitoring and continue for 12 hours post dose
9. Spirometry (FEV₁, FVC, and FEF₂₅₋₇₅), post administration of short-acting bronchodilator
10. Obtain blood samples for local laboratory assessments
11. Obtain urine sample for urinalysis (Time 0/pre-dose)
12. Obtain blood and urine samples for PK (Time 0/pre-dose)

Study Drug Administration:

Study drug to be administered by qualified site personnel via the designated study nebulizer, until all study drug solution has been administered. Subjects are to be seated during the entire

duration of study drug administration, inhaling the nebulized study drug using normal tidal breathing (no noseclips). Details regarding study drug preparation, device preparation and handling, as well as administration of study drug will be included in the Pharmacy Manual and Study Manual.

Post-dose:

1. Symptom-directed physical examination at 15, 60 minutes, 2, 4, 6, 8, and 12 hours post dose
2. Vital signs at 1, 10, 30, 60 minutes, 2, 4, and 12 hours post dose
3. Oximetry at 1, 10, 30, 60 minutes, 2, 4, and 12 hours post dose
4. Concomitant medications review
5. AE review
6. Spirometry at 10, 30, and 60 minutes, and 2, 4, and 8 hours post dose
7. Obtain blood samples for local laboratory assessments at 30, 60 minutes, 2, 4, 8, and 12 hours post dose
 - Complete blood count (CBC) with absolute differential
 - Serum chemistry
8. Obtain the following samples for PK:
 - Blood at 0.5, 1, 2, 3, 4, 12 hours post dose
 - Pooled urine from 0 to 4 hours and 4 to 12 hours post dose. Subjects should empty their bladders just prior to dosing and at the end of each time interval for the final urine collection of that interval. Urinalysis by dipstick will be performed on the pooled urine samples for each time interval.
 - Sputum at 3 times post dose, within the first 6 hours post dose. Suggest obtaining samples in conjunction with performing spirometry at 10, 60 minutes, and 4 hours post dose.
9. Discharge subject

